	ORR and DCR will be compared between treatment arms using Fisher's exact test and associated 95% CIs will also be derived. Time to deterioration of ECOG performance status to a score of 2 or higher will be analyzed as described for PFS. Change in QoL scores prior to cycles 2, 3 and 4 will be determined for the summary, all domains and single items by subtracting each patient's score from their corresponding baseline score. For each domain, the proportion of patients with deteriorating, stable or improving scores prior to cycles 2, 3 and 4 will be compared using Fisher's exact test. Time to QoL deterioration will be evaluated for each arm using Kaplan-Meier estimates and compared using the log-rank test.
	Safety Analyses
	Simple descriptive statistics will be provided for safety endpoints and demographic/baseline characteristics.
Sample Size Justification:	The study is designed to detect with 90% power a HR for death of 0.70 (30% risk reduction) in the TAS-102 arm compared with the placebo arm with an overall 1-sided type 1 error of 0.025. A variable accrual period of 18 months and a 5%/year loss to survival follow-up rate has been assumed. Using a treatment allocation of 2:1 (TAS-102:placebo) of 500 patients, 384 deaths will be targeted for the final OS analysis.
Interim Analyses:	One interim analysis for efficacy and futility is planned to be performed after approximately one-half of the total target events are observed.
Independent Data Monitoring Committee:	An independent Data Monitoring Committee (DMC) will periodically assess the cumulative safety data and results of the interim analysis and recommend study continuation, discontinuation, or study modification. A description of the roles and responsibilities of the DMC and details of the review processes and monitoring guidelines are provided in a separate DMC charter.

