13.3.2.3. Secondary Endpoint Analyses

All secondary endpoints comparisons will be made at the 2-sided 0.05 significance level. Since PFS is the only key secondary endpoint for regulatory registration purposes, no further multiplicity adjustments will be made. Assuming that OS demonstrates significance at the 1-sided 0.025 level, PFS can subsequently be tested at the 2-sided 0.05 level.

PFS

PFS will be analyzed with the methodology specified in Section 13.3.2.1 and Section 13.3.2.2a, c, and d. CCI

ORR and DCR

The treatment comparison for ORR and DCR will be based on the TR population using Fisher's exact test. Treatment estimates and differences will be presented along with the associated 95% CIs.

Time to Deterioration of ECOG Performance Status

Time to deterioration of ECOG performance status to a score of 2 or higher will be analyzed using methodology described in Section 13.3.2.1. Patients not reaching an ECOG of 2 or more (3, 4 or 5) will be censored at the last recorded ECOG assessment.

Quality of Life

Questionnaire compliance rates, for both scales, will be assessed at each measurement time point (baseline, prior to cycle 2, 3, 4, etc.).

Descriptive statistics, for both scales, for the summary scores, as well as the subscale scores will be provided for each assessed time point. In addition, change in QoL scores at representative time points will be determined for the summary, all domains and single items by subtracting each patient's score from their corresponding baseline score. Representative time points will be prior to cycle 2, 3 and 4, chosen based on expected patient compliance to be adequate to allow meaningful analyses, considering the expected treatment duration in the two study groups.

For each domain, the proportion of patients with deteriorating, stable or improving scores prior to cycles 2, 3 and 4 will be compared using Fisher's exact test. In addition, time to QoL deterioration will be evaluated for each arm using Kaplan-Meier estimates and compared using the log-rank test. The criteria for deteriorating, stable or improving scores will be detailed in the SAP.

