Key Secondary Efficacy Endpoint (PFS)

PFS will be evaluated from date of randomization to the first occurrence of radiologic progression or death. Treatment comparisons for PFS will use similar analytical methods as the OS endpoint.

Other Secondary Efficacy Endpoints

ORR and DCR will be compared between treatment arms using Fisher's exact test and associated 95% CIs will also be derived. Time to deterioration of ECOG performance status to a score of 2 or higher will be analyzed as described for PFS. Change in QoL scores prior to cycles 2, 3 and 4 will be determined for the summary, all domains and single items by subtracting each patient's score from their corresponding baseline score. For each domain, the proportion of patients with deteriorating (vs stable or improving) scores prior to cycles 2, 3 and 4 will be compared using Fisher's exact test. Time to QoL deterioration will be evaluated for each arm using Kaplan-Meier estimates and compared using the log-rank test.

Safety Analyses

Simple descriptive statistics will be provided for safety endpoints and demographic/baseline characteristics.

TABLE OF CONTENTS

1.	LIST OF ABBREVIATIONS.....	11
2.	INTRODUCTION.....	15
3.	STUDY OBJECTIVES AND ENDPOINTS.....	16
3.1.	Study Objectives.....	16
3.1.1.	Primary Objective.....	16
3.1.2.	Key Secondary Objectives.....	16
3.1.3.	Other Secondary Objectives.....	16
3.2.	Study Endpoints.....	16
3.2.1.	Primary Efficacy Endpoint.....	16
3.2.2.	Key Secondary Efficacy Endpoints.....	17
3.2.3.	Other Secondary Efficacy Endpoints.....	17
4.	STUDY DESIGN.....	19
4.1.	Summary of Study Design.....	19
4.2.	Definition of Study Drugs.....	20
4.3.	Sample Size Considerations.....	21
4.3.1.	Sample Size Justifications.....	21
4.4.	Randomization.....	21
4.5.	Clinical Assessments.....	21
4.5.1.	Vital Signs, Height and Weight.....	21
4.5.2.	Performance Status.....	21
4.5.3.	Laboratory Evaluations.....	22
4.5.4.	Pregnancy Testing.....	22
4.5.5.	Quality of Life.....	23
4.5.6.	Tumor Measurements.....	23
4.5.7.	Concomitant Medications.....	24
5.	PLANNED ANALYSES.....	25
5.1.	Interim Analyses.....	25
5.2.	Final Analyses.....	25
6.	STUDY DURATION AND VISIT SCHEDULE.....	26
7.	ANALYSIS POPULATIONS.....	29
7.1.	Intent-To-Treat (ITT) Population.....	29

7.2.	As-Treated (AT) Population (Safety Population).....	29
7.3.	Tumor Response(TR) Population.....	29
8.	DERIVED AND TRANSFORMED DATA	30
8.1.	Age (relatively to Informed Consent Date).....	30
8.2.	Study Day	30
8.3.	Baseline.....	30

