10.4.4. Other Secondary Efficacy Analysis

All other secondary endpoints comparisons will be made at the 2-sided 0.05 significance level.

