10.4.4.4.4. Analysis – Descriptive Statistics

Descriptive statistics (for all measures - both multi-item scales and single-item ones) for the summary scores, will be provided for each assessed time point. The statistics will include number of subjects, number of non-missing/missing scales, mean, standard deviation, median, minimum

and maximum. The results will be summarized for the actual and change from baseline values for all available scales and study visit time points.

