10.4.4.4.5. Deterioration vs Stable Proportion

For each EORTC QLQ-C30 and QLQ-STO22 score, deterioration in QoL will be defined as a decrease in the score from baseline level of at least five points, the threshold proposed by Osoba et al. [21] as a small but meaningful change in QoL. For each EORTC QLQ-30 and QLQ-STO22 measure, the proportion of patients with deteriorating and (stable or improving) scores at weeks 4, 8 and 12 will be compared using Fisher's exact test. The results will be summarized as a separate table.

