10.4.4.4.6. Time to Deterioration – Main Analysis

Time to first deterioration in QoL (refer to [Section 10.4.4.4.5](#) for definition) will be evaluated for each arm using Kaplan-Meier estimates and compared using the log-rank test (and Cox proportional hazards models adjusting for the baseline value of the EORTC QLQ-C30 and QLQ-STO22 score, country and primary tumour type). Patients with no deterioration in EORTC QLQ-C30 and QLQ-STO22 scores will be censored at the end of study, cut-off date or death date.

CCI

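### The protocol compares deteriorating, stable and improving QoL scores, but the SAP pools stable with improving and, in its readable text, defines only deterioration, so no between-arm comparison of improvement is planned

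*SAP*

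**What the plan says.** **Protocol.** The synopsis plans, domain by domain, that "the proportion of patients with deteriorating, stable or improving scores prior to cycles 2, 3 and 4 will be compared"; the named method is the Fisher test. Section 13.3.2.3 repeats this and adds: "The criteria for deteriorating, stable or improving scores will be detailed in the SAP".

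**SAP.** The synopsis keeps Fisher's test but compares "the proportion of patients with deteriorating (vs stable or improving) scores prior to cycles 2, 3 and 4". Section 10.4.4.4.5 does the same for "the proportion of patients with deteriorating and (stable or improving) scores at weeks 4, 8 and 12". The only criterion there is that "deterioration in QoL will be defined as a decrease in the score from baseline level of at least five points". No readable SAP text gives a threshold for improving or for stable.

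Two other SAP sections bear on the point:

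- 10.4.4.4.6 analyses "Time to first deterioration in QoL", so the other between-arm QoL analysis also concerns deterioration only.
- 10.4.4.4.4 provides descriptive statistics: "The results will be summarized for the actual and change from baseline values for all available scales and study visit time points".

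SAP 10.4.4 sets the level: "All other secondary endpoints comparisons will be made at the 2-sided 0.05 significance level".

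**The concern.** The protocol names three outcomes and commits the SAP to defining each of them. The SAP defines one and merges the other two. A patient whose score rises by 30 points on a scale where higher is better falls in the same category as a patient with no change.

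QoL is a named secondary objective in both documents. If the arms differed mainly in how many patients improve, the protocol's comparison could show it and the SAP's could not. A reader holding the protocol would expect a proportion improved in the report, and the SAP as written would not produce one.

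**Working it through.** The documents give no rate, power or evaluable number for the QoL comparison, so there is no stated figure to reproduce. The check has two parts: the texts side by side, then an illustration of how the two tests differ.

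**1. Texts side by side**

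| Item | Protocol (synopsis, 13.3.2.3) | SAP (synopsis, 10.4.4.4.5) |
|---|---|---|
| Categories | deteriorating, stable, improving | deteriorating v the rest |
| Criteria | all three left to the SAP | deterioration only |
| Test | Fisher's exact | Fisher's exact |
| Times | before cycles 2, 3, 4 | synopsis: before cycles 2, 3, 4; body: weeks 4, 8, 12 |

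The pooling is stated in unredacted text in two places of the SAP. The time labels are a separate matter: they coincide only if no cycle is delayed.

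**2. Why pooling is blind to improvement**

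The two-category table depends on the data only through the number deteriorating in each arm. Moving patients between stable and improving leaves it unchanged. This needs no assumed rate.

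Worked example (assumed): 200 v 100 patients with scores, 40% deteriorating in both arms, 25% v 10% improving.

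- Counts (deteriorating/stable/improving): 80/70/50 v 40/50/10.
- Pooled table: 80/120 v 40/60, identical proportions. Fisher p = 1.00.
- Three-category table: column totals 120/120/60, expected counts 80/80/40 and 40/40/20. Pearson statistic = 0 + 100/80 + 100/40 + 0 + 100/40 + 100/20 = 1.25 + 2.5 + 2.5 + 5 = 11.25 on 2 df, so p = exp(−11.25/2) = 0.004. The exact (Fisher-Freeman-Halton) p is 0.003.

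**3. Power under assumed rates** (simulation, 2-sided 0.05)

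Exact tests on both tables, 1,500 trials per case:

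| Deteriorating | Improving | Patients | Two-category | Three-category |
|---|---|---|---|---|
| 40% v 40% | 25% v 10% | 333 v 167 | 0.04 | 0.99 |
| | | 200 v 100 | 0.04 | 0.90 |
| | | 100 v 50 | 0.04 | 0.57 |
| 40% v 55% | 20% v 20% | 200 v 100 | 0.67 | 0.71 |
| 40% v 50% | 25% v 15% | 200 v 100 | 0.35 | 0.49 |

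The 333 v 167 split is all 500 patients at 2:1; the smaller splits allow for patients without scores.

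Two-category Fisher against a three-category Pearson test (standing in for the exact test), 220 v 100 patients, 3,000 trials per case:

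| Deteriorating/stable/improving (%) | Two-category | Three-category |
|---|---|---|
| 40/35/25 v 45/42/13 | 12% | 60% |
| 40/36/24 v 55/27/18 | 67% | 59% |
| 40/40/20 v 55/30/15 | 67% | 60% |

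In the last two rows the stable-to-improving ratio is the same in both arms (36:24 = 27:18 = 1.5; 40:20 = 30:15 = 2). The third category then carries no treatment information and costs a degree of freedom. With no difference between arms, both tests reject in about 4% to 5% of trials.

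**4. Number of comparisons**

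SAP 10.4.4.4 lists 5 + 3 + 1 + 6 = 15 QLQ-C30 measures and 5 + 4 = 9 QLQ-STO22 measures: 24 in all. At three time points, one added test each gives 24 × 3 = 72.

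**The case against.** The case for leaving the SAP alone has several parts.

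- **Improvement is still reported.** A reader might infer that QoL improvement cannot be shown at all. The documents do not support that: SAP 10.4.4.4.4 summarises change from baseline for every scale and visit. What is missing is a proportion improved and a between-arm comparison of it.
- **The protocol does not specify one 2×3 test.** It could equally mean several 2×2 tests. This stands, but on either reading the SAP covers only the deterioration contrast.
- **The pooling looks deliberate.** The SAP synopsis, 10.4.4.4.5 and the time-to-deterioration analysis all centre on deterioration, and SAP Section 2 places analysis decisions before unblinding. This stands: it is a prespecified choice, not one left to the analyst. It is still an unexplained departure from the protocol in the readable text.
- **SAP Section 14.** Its readable text does not mention the pooling, and a reader might infer an undeclared late change. That does not follow: the list covers only changes since SAP version 1.05, and part of it is redacted.
- **Redaction.** Text after 10.4.4.4.6 and the appendices are blacked out, so further definitions there cannot be excluded. The pooled comparison itself is readable, so its conflict with the protocol remains.
- **Power can go either way.** A reader might infer that three categories are always more sensitive. They are not, as the equal-ratio cases show.

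**Conclusion.** The discrepancy is real. The protocol's three-way comparison becomes deterioration versus the rest, and two of the three promised criteria are absent from the readable SAP. As a result no proportion improved is defined, and no comparison of improvement between arms is planned.

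Blindness to an improving-versus-stable difference follows from the pooling alone. Its cost in power rests entirely on assumed rates and evaluable numbers. It is large when improvement differs (for example 12% v 60%), small or moderate when deterioration carries the effect (0.67 v 0.71), and reversed when the stable-to-improving ratio is equal (67% v 59%). The case for change is therefore fidelity to the protocol and a reportable improvement result, not a general gain in power.

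QoL is an other-secondary endpoint without multiplicity control. OS and PFS conclusions are unaffected.

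**What to change.** In SAP 10.4.4.4.5, define three mutually exclusive categories for each scale:

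- deterioration: a change of at least 5 points in the adverse direction of that scale;
- improvement: a change of at least 5 points in the beneficial direction;
- stable: anything between.

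This must replace the present definition of deterioration as a decrease in every score. If that wording stayed and improvement were added by beneficial direction, a 5-point fall on any scale where lower is better would count as both.

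Then tabulate all three proportions by arm and time point, and report the protocol's comparison of them, stating whether it is one three-category test or separate contrasts. Keep deterioration versus the rest as the existing display, and label the added comparisons as unadjusted. Amend the SAP synopsis to match.

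The cost is SAP wording, an added row per table and, if tested, one more unadjusted test per scale at each of three time points, about 72 in all. No new data are needed. If the sponsor prefers to keep the pooling, the minimum is to state and justify it in the SAP as a change from protocol 13.3.2.3.

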10.4.4.4.6. Time to Deterioration – Main Analysis

Time to first deterioration in QoL (refer to [Section 10.4.4.4.5](#) for definition) will be evaluated for each arm using Kaplan-Meier estimates and compared using the log-rank test (and Cox proportional hazards models adjusting for the baseline value of the EORTC QLQ-C30 and QLQ-STO22 score, country and primary tumour type). Patients with no deterioration in EORTC QLQ-C30 and QLQ-STO22 scores will be censored at the end of study, cut-off date or death date.

CCI

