4. STUDY DESIGN

4.1. Summary of Study Design

This is a multinational, double-blind, two-arm, parallel, randomized, Phase 3 study evaluating the efficacy and safety of TAS-102 plus BSC versus placebo plus BSC in patients with metastatic gastric cancer who have received at least 2 prior regimens for advanced disease. The study will be conducted under the sponsorship of Taiho Pharmaceutical Co., Ltd. for sites in Japan and Taiho Oncology, Inc. for sites in the rest of the world (ROW).

Eligible patients will be centrally randomized (2:1) to TAS-102 + BSC (experimental arm) or placebo + BSC (control arm) using a dynamic allocation method (biased coin) via an Interactive Voice/Web Response System (IXRS), stratified by:

- Region (ROW1 vs. Japan)
- ECOG PS (0 vs. 1)
- Prior treatment with ramucirumab (yes vs. no)

Study medication should be started within 3 calendar days after the date of randomization and continue until a discontinuation criterion is met or until completion of the primary endpoint analysis, whichever is sooner.

TAS-102 (35 mg/m²/dose) or placebo will be administered orally BID, within 1 hour after completion of morning and evening meals, for 5 days a week with 2 days rest for 2 weeks, followed by a 14-day rest, repeated every 4 weeks [1, 2, 3, 4, 5, 6, 7].

Computed tomography (CT) scans will be performed at baseline and every 8 weeks thereafter until disease progression. On-site tumor assessments will be performed by the Investigator/local radiologist. Tumor assessments will be analyzed using Response Evaluation Criteria in Solid Tumors (RECIST) criteria (Version 1.1, 2009). If patient discontinuation is for reasons other than radiologic disease progression (i.e., with intolerable side effects), patients will be followed every 8 weeks for tumor response until radiologic disease progression or initiation of new anticancer therapy (whichever occurs first).

Quality of life assessments (EORTC QLQ-C30 and QLQ-STO22) will be performed prior to start of dose administration in each cycle.

Flow chart of the Study is presented in the Figure 1.

[figure not shown]

Figure 1. Flow chart of the Study.

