10.4. Analysis of the Primary Efficacy Endpoint

10.4.1. Primary Efficacy Analysis

OS in the ITT population will be compared between the 2 treatment groups (ITT population) using the stratified log-rank test (based on PROC LIFETEST, CCI  ). One- and 2-sided p-values will be presented. The study will be declared to have met its primary objective if the 1-sided p-value is be less than 0.0215 (please refer to [Section 12](#) for more details). The estimate of the hazard ratio (HR) and corresponding 95% CI will be provided using a Cox proportional hazards (CPH) model including treatment and the 3 stratifications factors in the model. Survival for each arm will be summarized using Kaplan Meier curves and further characterized in terms of the median and survival probability at 3, 6, 9 and 12 months, along with the corresponding 2-sided 95% CI for the estimates. The stratification factors will be populated as per the IXRS assignment.

Confidence intervals for median survival are based upon the methods of Brookmeyer and Crowley [16]. Confidence intervals for survivorship estimates are calculated using the log-log transformation [17] where the estimated variance of $\log(-\log(\hat{S}(t)))$ is:

$$\tau^2(t) = \sigma^2[\hat{S}(t)] / [\hat{S}(t)\log(\hat{S}(t))]^2 .$$

The 100 x (1- α)% confidence interval for $S(t)$ is given by:

$$[\hat{S}(t)]^{\exp(z_{\alpha/2}\tau(t))} \leq S(t) \leq [\hat{S}(t)]^{\exp(-z_{\alpha/2}\tau(t))}$$

CCI

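### Time to QoL deterioration: no stratification is stated for the log-rank test, and the Cox model leaves out ECOG PS and prior ramucirumab

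*SAP*

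**What the plan says.** SAP Section 10.4.4.4.6, titled as the main analysis of time to deterioration, estimates time to first deterioration by Kaplan-Meier. The arms are "compared using the log-rank test", and a parenthesis adds "Cox proportional hazards models adjusting for the baseline value of the EORTC QLQ-C30 and QLQ-STO22 score, country and primary tumour type". The section does not refer back to the OS method.

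Protocol Section 13.3.2.3 says for the same endpoint that "time to QoL deterioration will be evaluated for each arm using Kaplan-Meier estimates and compared using the log-rank test". It mentions neither stratification nor a Cox model.

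SAP Section 4.1 describes dynamic (biased coin) allocation, 2:1, on three factors: region (Japan or elsewhere), ECOG PS (0 or 1) and prior ramucirumab (yes or no).

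For OS, SAP Section 10.4.1 compares the arms "using the stratified log-rank test" and takes the HR from a Cox "model including treatment and the 3 stratifications factors in the model", with factor values from IXRS. PFS (Section 10.4.3) and time to ECOG deterioration (Section 10.4.4.3) are both sent back to Section 10.4.1.

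**The concern.** The factors that the allocation balances should normally enter the analysis. If they predict the outcome, leaving them out costs power and pulls the estimated HR toward 1. ECOG PS is a plausible predictor of QoL decline. The choice is repeated across scales: by SAP Section 10.4.4.4 the QLQ-C30 has 5 + 3 + 1 + 6 = 15 measures and the QLQ-STO22 has 5 + 4 = 9, which makes 24 analyses.

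The test and the HR for one scale would also come from different adjustment sets. The log-rank test names no factor, while the Cox model uses baseline score, country and tumour type. In Section 10.4.1 both use the same three factors.

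**Working it through.** **Step 1. Side by side.**

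| Endpoint | SAP section | Test | Cox model |
|---|---|---|---|
| OS | 10.4.1 | stratified log-rank | treatment + 3 IXRS factors |
| PFS | 10.4.3 | as 10.4.1 | as 10.4.1 |
| Time to ECOG PS of 2 or more | 10.4.4.3 | as 10.4.1 | as 10.4.1 |
| Time to QoL deterioration | 10.4.4.4.6 | log-rank, stratification not mentioned | baseline score, country, tumour type |

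**Step 2. How to read the bare log-rank test.** The SAP writes *stratified* in Section 10.4.1 and *unstratified* in Section 10.4.2.1. A log-rank test with neither word and no cross-reference is most naturally read as unstratified, but this is an inference. The general rule that opens SAP Section 10 sets the source of the factor values (IXRS). It does not say that every test is stratified.

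**Step 3. Which factors the Cox model lacks.** Region is Japan against the rest of the world, so a patient's country fixes the region, and country terms absorb it. ECOG PS and prior ramucirumab have no such stand-in. Two of three factors are missing.

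**Step 4. Figures in the plan.** The plan gives no power, effect size or event count for this endpoint, so there is none to reproduce. The only stated power is for OS. With 384 deaths, 2:1 allocation, HR 0.70 and 1-sided 0.025: √(384 × 2/9) × |ln 0.70| = 9.238 × 0.3567 = 3.295, and Φ(3.295 − 1.960) = 0.909, in line with the stated 90%. Nothing in that figure depends on the present point.

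**Step 5. Size of the effect.** Every input here is an assumption except N = 500 and 2:1, which are the plan's:

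- true HR 0.75, 2-sided 0.05
- control median 2.5 months at average factor values, exponential censoring with median 4 months
- factor prevalences: Japan 15%, ECOG PS 1 60%, prior ramucirumab 33%, giving 8 strata
- 2:1 blocks of three within each stratum, to imitate the balance of the dynamic allocation
- 3,000 simulated trials per setting

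Hand check of the setting without prognostic factors. The event probability is hazard / (hazard + censoring rate).

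- Control: 0.2773 / (0.2773 + 0.1733) = 0.615.
- TAS-102: 0.2079 / (0.2079 + 0.1733) = 0.545.
- Expected events: 166.7 × 0.615 + 333.3 × 0.545 ≈ 284.
- √(284 × 2/9) × |ln 0.75| = 7.95 × 0.2877 = 2.29, and Φ(2.29 − 1.96) = 0.63, which agrees with the simulated 63%.

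| HR of each factor | Power, unstratified | Power, stratified | Type I error, unstratified | Type I error, stratified |
|---|---|---|---|---|
| 1.0 | 63% | 61% | 4.2% | 4.6% |
| 1.5 | 62% | 64% | 5.1% | 5.8% |
| 2.0 | 53% | 60% | 3.6% | 5.7% |

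The simulation standard error is √(0.6 × 0.4 / 3,000) ≈ 0.9 points for power and √(0.05 × 0.95 / 3,000) ≈ 0.4 points for type I error. In the strongest case the mean log-rank estimate of the HR is 0.739 stratified and 0.767 unstratified, so leaving the factors out moves it toward 1. The small loss in the first row fits thin strata: with these prevalences the smallest cell holds 500 × 0.15 × 0.40 × 0.33 ≈ 10 patients.

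**The case against.** The case for leaving the text alone has several sound parts.

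- **Silence.** A reader might infer that the SAP prescribes an unstratified test. It does not say so; Section 10.4.2.1 only makes that the likelier reading. This stands, and it is itself a reason to clarify.
- **Protocol and SAP agree.** Both name only the log-rank test for this endpoint, and the Cox model is an SAP addition. There is no conflict between the documents.
- **The other endpoints are not uniform.** A reader might infer that every other time-to-event comparison is stratified. Time to the first, second and third tumour assessment (SAP Section 10.4.3) also gets a plain log-rank test, and time to worst laboratory grade (Section 11.6) gets only Kaplan-Meier estimates. The contrast holds for OS, PFS and time to ECOG deterioration.
- **Country terms.** A reader might infer that they make the model unstable. SAP Section 8.14 lists 15 countries as EU for this study; with the US and Japan that makes 17, or up to 16 parameters if all enrolled. Enrolment by country is not given, so instability is possible but not shown.
- **Redaction.** Blacked-out text follows the section. Further QoL analyses may be there and cannot be counted as missing.
- **Stakes.** QoL is an other secondary endpoint, and PFS is the only key secondary efficacy endpoint for registration. No primary or key secondary conclusion changes.

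What remains is that the readable main analysis omits two randomization factors without a reason, and that the form of the test is left to inference.

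**Conclusion.** The point holds as a low-cost improvement. The main analysis of time to QoL deterioration states no stratification, and its Cox model lacks ECOG PS and prior ramucirumab. It should not be read as dropping all three randomization factors, since country carries region in the Cox model. Nor does it ignore baseline QoL, which is already a covariate.

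The gain from stratifying depends on how prognostic the factors are, which the documents do not say. Under the stated assumptions it runs from a slight loss (63% to 61%) through 62% to 64%, up to 53% to 60%. A reader might infer that the planned comparison is invalid. The simulation does not support that: unstratified type I error was 3.6% to 5.1%. The cost is power and some shrinkage of the HR toward 1, on an endpoint without multiplicity control.

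**What to change.** In SAP Section 10.4.4.4.6, before unblinding:

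1. State that the log-rank test is stratified by the three IXRS factors.
2. Include those factors in the Cox model, as strata or as covariates, together with the planned baseline score, specified as that of the same scale.
3. Keep the model with country and primary tumour type as a sensitivity analysis if it is wanted. Give it a rule for sparse countries and tie tumour type to a defined variable; the nearest in the readable text is the primary cancer type in Section 9.5.1.

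If the sponsor prefers the present covariates, the alternative is to say whether the test is stratified and why ECOG PS and ramucirumab are left out.

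The cost is SAP wording and minor programming. The factors are already held in IXRS, so no new data, patients or follow-up are needed.
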